	Discontinuation form} - Start date of Axitinib + 1) / 30.44 , if more than 1 case described above is reported
	Else, the time to treatment failure will be censored as follows:
	• (Maximum of { Date of last Axitinib follow-up visit ; Last visit date reported on the Study Discontinuation form whereas last treatment received is Axitinib } - Start date of Axitinib + 1)/30.44
	Note : Start date of Axitinib will be the one reported at time of Axitinib initiation visit (cf. CRF page 25 " Therapy started with Axitinib in 2nd line on ")

- Time to Treatment Failure (TTF) for the sequence Sunitinib-Axitinib

The TTF will be defined as the time when the patient receives the first dose with SU in 1st line to the time of AXI 2nd line treatment discontinuation (date completed by the physician), whatever the reason for discontinuation and whatever the following therapeutic strategy.

Variable name	Definition
TTF status	Patient will not be censored for the TTF analysis (TTF status = 1) in the following cases:
	 Axitinib discontinued due to Progression, Intolerability or Death (cf. CRF page 35)
	 Study Discontinuation for any reason except lost to follow-up or patient's request whereas last treatment received is Axitinib (cf. CRF page 37)
	In all other cases, patient will be censored for the TTF analysis (TTF status = 0).
	Note: Other reasons for Axitinib discontinuation as well as other reason for study discontinuation (whereas last treatment received is Axitinib) will be reviewed at time of DRMs in order to decide whether corresponding cases should be censored or not for TTF analysis

TTF status and TTF time will be calculated as detailed below:

Variable name	Definition
TTF time	The time to treatment failure will be calculated in months as:
(months)	• (Date of progression/intolerability or death reported at time of Axitinib discontinuation - Start date of Sunitinib + 1) / 30.44, if case n°1 described above is reported
	• (Date of death reported on the Study Discontinuation form - Start date of Sunitinib + 1) / 30.44, if case n°2 described above is reported and reason for study discontinuation is 'death'
	• (Axitinib end date reported on the Study Discontinuation form - Start date of Sunitinib + 1) / 30.44, if case n°2 described above is reported and reason for study discontinuation is not 'death' and Axitinib status at last visit is 'discontinued'

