	Note: as only month and year of Axitinib end are reported in such cases, day of Axitinib end will automatically be "forced" to 01
	• (Last visit date reported on the Study Discontinuation form - Start date of Sunitinib + 1) / 30.44, if case n°2 described above is reported and reason for study discontinuation is not 'death' and Axitinib status at last visit is 'ongoing'
	 (Minimum of {Date of progression/intolerability or death reported at time of Axitinib discontinuation ; Date of death reported on the Study Discontinuation form ; Axitinib end date reported on the Study Discontinuation form ; Last visit date reported on the Study Discontinuation form} - Start date of Sunitinib + 1) / 30.44, if more than 1 case described above is reported
	Else, the time to treatment failure will be censored as follows:
	 (Maximum of { Date of last Axitinib follow-up visit ; Last visit date reported on the Study Discontinuation form whereas last treatment received is Axitinib } - Start date of Sunitinib + 1) / 30.44
	Note: Start date of Sunitinib will be the one reported:
	- at time of Sunitinib initiation visit for patients enrolled at SU initiation (cf. CRF page 11 "Therapy started with Sunitinib in 1st line on")
	- at time of Axitinib initiation visit for patients enrolled at AXI initiation (cf. CRF page 26 "Therapy started with Sunitinib in 1st line on")

6.1.2 Secondary Endpoints

- Time to Strategy Failure (TSF) for the sequence Sunitinib-Axitinib

The TSF will be defined as the time from when the patient receives the first dose with SU in first line to the time of AXI 2nd line treatment discontinuation (date completed by the physician) without the time between discontinuation of SU and start of the 2nd line AXI treatment.

TSF status will be the same as TTF status for the sequence Sunitinib-Axitinib.

TSF time will be equal to:

- For patients enrolled at SU initiation : TTF time (Start date of Axitinib reported at time of Axitinib initiation visit Date of progression/intolerability/death reported at time of Sunitinib discontinuation)
- For patients enrolled at AXI initiation : TTF time (Start date of Axitinib reported at time of Axitinib initiation visit Date of Sunitinib end reported at time of Axitinib initiation visit*)

*cf. CRF page 26 "Therapy with Sunitinib in first line; therapy discontinuation on"

- Overall Survival (OS) for the sequence Sunitinib-Axitinib

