• Kaplan-Meier estimates (product-limit estimates) will be presented with a summary of associated statistics: number of events, number of censored data, median survival time, Q1 and Q3 survival times and survival rates every 3 months.

The confidence intervals for the median, Q1 and Q3 will also be provided according to Brookmeyer and Crowley (1982)

• The Kaplan-Meier curve will also be presented

Other primary endpoints will be analyzed according to the same methods:

- PFS for the sequence Sunitinib-Axitinib in the SU-AXI subgroup
- TTF under Axitinib in 2nd line post Sunitinib in the SU-AXI subgroup
- TTF for the sequence Sunitinib-Axitinib in the SU-AXI subgroup

Additionally a Cox regression model will run for the PFS under Axitinib in 2nd line post Sunitinib in the SU-AXI subgroup according to the method described in section 8.1 of this document (Strategy of selection of variables in multivariate models). Potential factors to be tested will be defined at time of Data Review Meetings among the ones mentioned in section 6.4 of this document.

Secondary endpoints

TSF for the sequence Sunitinib-Axitinib will be described using the Kaplan Meier method in the SU-AXI subgroup:

• Kaplan-Meier estimates (product-limit estimates) will be presented with a summary of associated statistics: number of events, number of censored data, median survival time, Q1 and Q3 survival times and survival rates every 3 months.

The confidence intervals for the median, Q1 and Q3 will also be provided according to Brookmeyer and Crowley (1982)

• The Kaplan-Meier curve will also be presented

Following secondary endpoints will be analyzed according to the same methods:

- OS for the sequence SU-AXI in the SU-AXI subgroup
- PFS for Sunitinib received in 1st line
- OS for Sunitinib received in 1st line

ORR under Axitinib in 2nd line post Sunitinib will be given with its 2-sided 95% 'exact' Clopper-Pearson confidence interval in the SU-AXI subgroup.

Same analysis will be done for:

- CBR under Axitinib in 2nd line post Sunitinib in the SU-AXI subgroup
- ORR for Sunitinib received in 1st line
- CBR for Sunitinib received in 1st line

Additionally, following analysis will be performed according to MSKCC prognosis classification at Axitinib initiation (good/intermediate/poor) using the Kaplan Meier method:

- PFS under Axitinib in 2nd line post Sunitinib in the SU-AXI subgroup
- ORR under Axitinib in 2nd line post Sunitinib in the SU-AXI subgroup

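### The time to strategy failure (TSF) derivation takes an unconverted date difference from a time in months, so as written it over-subtracts the gap between lines 30.44-fold

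*SAP*

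**What the plan says.** SAP 6.1.1 sets the unit of TTF for the sunitinib-axitinib sequence: "The time to treatment failure will be calculated in months as". Each formula beneath it is a date difference plus one day, divided by 30.44. The first reads "Date of progression/intolerability or death reported at time of Axitinib discontinuation - Start date of Sunitinib + 1) / 30.44".

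SAP 6.1.2 defines TSF in words as the same interval "without the time between discontinuation of SU and start of the 2nd line AXI treatment". Protocol 8.1.1 (Study endpoints) and 8.7.1 give the same verbal definition and no formula.

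The SAP then gives one TSF formula per cohort:

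- Enrolled at sunitinib initiation: the line opens "For patients enrolled at SU initiation : TTF time (Start date of Axitinib reported at time of Axitinib initiation visit", and its formula in full is "TTF time (Start date of Axitinib reported at time of Axitinib initiation visit Date of progression/intolerability/death reported at time of Sunitinib discontinuation". The bracket closes there.
- Enrolled at axitinib initiation: "TTF time (Start date of Axitinib reported at time of Axitinib initiation visit Date of Sunitinib end reported at time of Axitinib initiation visit". An asterisk to a CRF field and the closing bracket follow.

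Neither line divides the bracket by 30.44, and neither states a unit for the bracket or for TSF.

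On use, SAP 8.2.2 says "TSF for the sequence Sunitinib-Axitinib will be described using the Kaplan Meier method in the SU-AXI subgroup", with median, quartiles and 3-monthly rates.

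**The concern.** The difference between two calendar dates is naturally a number of days. If it is taken from a quantity in months without conversion, the result has no consistent unit.

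TSF exists to remove the time between the two drugs from the sequence. With the conversion missing, that gap would dominate the endpoint instead of dropping out of it. The error is zero for a patient with no gap and grows with the gap, so the distortion would fall on patients with the longest interval between lines.

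These two lines are the only TSF derivation in the documents. SAP Appendix 2 is marked not applicable, and the table shells are held in separate documents (SAP 9). A programmer, or a second programmer working independently from the same text, would have nothing else to follow.

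**Working it through.** The documents give no numerical TSF, so there is no figure to reproduce. The check is one of units.

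**Inputs from the SAP**

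- TTF (months) = (axitinib end - sunitinib start + 1) / 30.44, from 6.1.1.
- Gap = axitinib start - sunitinib end, from the brackets in 6.1.2.
- The operation is subtraction. The minus signs are missing from the text as read, but the verbal definition leaves no doubt.

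**The two readings**

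- Literal: TSF = TTF - gap.
- Consistent units: TSF = TTF - gap / 30.44.

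One gap day lowers literal TSF by 1 and consistent TSF by 1 / 30.44 = 0.033 month, a ratio of 30.44. Literal TSF is below zero when gap days exceed TTF months, that is, when the gap exceeds 1 / 30.44 = 3.3% of the whole sequence time.

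**Single patients, assumed values (TTF 18.0 months)**

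| Gap (days) | Literal | Consistent units |
|---|---|---|
| 5 | 18 - 5 = 13.0 | 18 - 0.16 = 17.8 |
| 21 | 18 - 21 = -3.0 | 18 - 0.69 = 17.3 |

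**Same time on treatment, varying gap.** Sunitinib 9 months is assumed. Axitinib 6.5 months uses, as a proxy for duration, the investigator-assessed PFS after sunitinib quoted in Protocol section 6. Days on treatment: 15.5 x 30.44 = 471.82.

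| Gap (days) | TTF (months) | Literal TSF | Consistent TSF |
|---|---|---|---|
| 0 | 472.82 / 30.44 = 15.53 | 15.53 | 15.53 |
| 14 | 486.82 / 30.44 = 15.99 | 1.99 | 15.53 |
| 28 | 500.82 / 30.44 = 16.45 | -11.55 | 15.53 |

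The converted version does not move with the gap, as the definition intends. The literal version moves almost one unit per day.

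**How often negative?** This needs inputs that the documents do not give. A simulation of 200,000 patients per scenario assumed exponential durations (sunitinib median 6, 9 or 11 months; axitinib median 4.8 or 6.5 months, the AXIS PFS values again used as proxies) and a lognormal gap with sigma 0.8. The share negative was:

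| Assumed median gap (days) | Share negative |
|---|---|
| 3 | 6-11% |
| 7 | 18-30% |
| 14 | 37-53% |
| 21 | 51-67% |
| 28 | 61-77% |
| 42 | 74-87% |

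The answer is driven almost entirely by the assumed gap.

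**The case against.** **The intent is clear.** The verbal definition is sound, and the bracket can be read as simply naming the interval to be removed. That is fair: the endpoint concept is not at fault. But the line is written as an equation on a variable already defined in months, and it states no unit.

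**The divisor may have been lost in text extraction.** Minus signs are missing from these same lines, and a bracket is unbalanced in the retrospective sunitinib PFS formula. Certainty is therefore not warranted, and the source PDF should be looked at. Still, the divisor is printed in every other time formula of SAP 6.1 and is absent from both TSF lines, so two separate losses in exactly these places are unlikely. The missing minus signs are probably an extraction loss and are not raised as an error.

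**A programmer would notice.** Negative values would probably be caught, although the documents describe no such check. A 5-day gap is harder to catch: 13.0 instead of 17.8 months looks plausible.

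**Stronger readings.** A reader might infer that TSF would often be negative. The documents do not support this, because they give no gap lengths and no sunitinib durations; the simulated range of 6% to 87% only reflects what was assumed. A reader might also infer that the gap should start from the last sunitinib dose. The CRF sections that the SAP uses for the end of sunitinib record a discontinuation date, or a date of progression, intolerability or death, and no last-dose date.

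**Conclusion.** The point holds as a specification error: as written, both TSF formulas subtract days from months. TSF is wrong for every patient whose axitinib start date differs from the sunitinib end date, with the gap over-subtracted 30.44-fold. It is negative whenever the gap in days exceeds TTF in months. The frequency of negative values cannot be determined from the documents.

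This rests on two assumptions: that the bracket is a plain date difference in days, and that no divisor was lost from the two lines in extraction. The worked patients use assumed values and show scale only.

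The effect is confined to one descriptive secondary endpoint, to which SAP 4.2 attaches no decision rule. PFS, TTF and OS have their own formulas and are unaffected. It should be corrected before programming, but it does not threaten the primary results.

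**What to change.** In both lines of SAP 6.1.2 write: TSF (months) = TTF (months) - (axitinib start date - sunitinib discontinuation date) / 30.44. Keep the sunitinib date already specified for each cohort, and state that TSF is in months.

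The cost is a one-line correction in each of two places, with no new data and no change to any other endpoint. If TSF has already been programmed, confirm that the code divides the gap by 30.44.

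One residue can be left alone: if the sunitinib end date and the axitinib start date both count as treatment days, the corrected TSF is one day (0.03 month) short.

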8.1.1. Study endpoints

Primary endpoints:

Progression Free Survival (PFS):

- PFS for patients with adv/mRCC receiving AXI in 2nd line post SU as defined as the time from when the patient receives the first dose of AXI to the time of progression or death due to any cause, whichever occurs first
- Combined PFS for patients with adv/mRCC receiving the SU-AXI sequence as defined
 as the time from when the patient receives the first dose with SU in first line, until
 progression or death due to any cause with AXI in 2nd line, whichever occurs first during
 the SU-AXI sequence

(Time to Treatment Failure) TTF:

- TTF for the AXI 2nd line as defined as from when the patient receives the first dose of AXI to the time of AXI discontinuation (date completed by the physician).
- TTF for the SU-AXI sequence as defined as the time from when the patient receives the first dose with SU in first line to the time of AXI discontinuation (date completed by the physician).

Secondary endpoints:

- Objective Response Rate (ORR) for adv/mRCC patients receiving AXI in 2nd line post SU defined as the percentage of patients with confirmed complete response (CR) or confirmed partial response (PR) according to RECIST criteria v1.1.
- Overall survival (OS) for adv/mRCC patients receiving SU in first line followed by AXI in 2nd line as measured from date of first SU dose to the date of death of any cause. The OS median and the overall survival at month 24 (24 month OS) will be measured.
- Time to strategy failure (TSF) for patients receiving the SU-AXI sequence is defines as the time from when the patient receives the first dose with SU in first line to the time of AXI discontinuation (date completed by the physician) without the time between discontinuation of SU and start of AXI.
- Description of real life usage of flexible dosing across Europe with description of treatment schedules (dosing change, dosing schedule, average dose received during the period treatment)

- Proportion of titrated patients: titration is defined as described in the SmPC. A patient is considered as titrated when an AXI dose increase is maintained for at least 4 weeks.
- PFS for titrated and non-titrated patients when they receive AXI in 2nd line post SU
- Efficacy parameters (PFS, OS) for the combined 1st line SU 2nd line sequences according to the second line post Sunitinib (other than SU-AXI):
 - SU in 1st line other TKI in 2nd line (sorafenib, pazopanib)

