Similar to PFS, Kaplan-Meier analyses will be performed for TTF and TSF.

Objective Response Rate (ORR)

ORR is defined as the percentage of patients with confirmed complete response (CR) or confirmed partial response (PR) according to RECIST V1.1, relative to all patients who have baseline measurable disease. Confirmed responses are those that persist on repeat imaging study \geq 4 weeks after initial documentation of response.

Patients who die, progress, or drop out for any reason prior to reaching a CR or PR will be counted as non-responders in the assessment of ORR. A patient, who initially meets the criteria for a PR and then subsequently becomes a confirmed CR, will be assigned a best response of CR.

ORR will be assessed and a 2-sided 95% confidence interval will be provided using the Clopper-Pearson formula.

Overall Survival (OS)

OS is defined as the date from first SU dose to the date of death due to any cause. For patients not experiencing the event, their survival times will be censored at the last date they are known to be alive. Similar to PFS, Kaplan-Meier analyses will be performed for OS. The share of patients alive (OS) at 2 year will be measured for the sequence.

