The OS will be defined as the time from date of first SU dose to the date of death of any cause. For patients not experiencing the event, their survival times will be censored at the last date they are known to be alive

Variable name	Definition
OS status	Patient will not be censored for the OS analysis (OS status = 1) in the following cases:
	1) Axitinib discontinued due to Death (cf. CRF page 35)
	2) Death reported in Long term Follow-up (cf. CRF page 36)
	 Death reported on the Study Discontinuation form (cf. CRF page 37)
	In all other cases, patient will be censored for the OS analysis (OS status $= 0$).

OS status and OS time will be calculated as detailed below:

Variable name	Definition					
OS time	The overall survival time will be calculated in months as:					
(months)	 (Date of death reported at time of Axitinib discontinuation - Start date of Sunitinib + 1) / 30.44, if case n°1 described above is reported 					
	 (Date of death reported in Long term Follow-up - Start date of Sunitinib + 1) / 30.44, if case n°2 described above is reported 					
	 (Date of death reported on the Study Discontinuation form - Start date of Sunitinib + 1) / 30.44, if case n°3 described above is reported 					
	Else, the overall survival time will be censored as follows:					
	 (Maximum of {All visits dates reported} - Start date of Sunitinib + 1) / 30.44 					
	Note: Start date of Sunitinib will be the one reported:					
	- at time of Sunitinib initiation visit for patients enrolled at SU initiation (cf. CRF page 11 " Therapy started with Sunitinib in 1st line on ")					
	- at time of Axitinib initiation visit for patients enrolled at AXI initiation (cf. CRF page 26 "Therapy started with Sunitinib in 1st line on")					

- Best Response under Axitinib in 2nd line post Sunitinib

Number and percentages of patients by best response (CR, PR, SD or PD) will be presented.

- Objective Response Rate (ORR) under Axitinib in 2nd line post Sunitinib

ORR is defined as the percentage of patients with complete response (CR) or partial response (PR) according to RECIST from the start to the end of Axitinib treatment (cf. CRF page 29).

Patients who die, progress, or drop out for any reason prior to reaching a CR or PR will be counted as non-responders in the assessment of ORR.

All assessments following an assessment of PD will be excluded from the derivation of ORR.

- Clinical benefice Rate (CBR) under Axitinib in 2nd line post Sunitinib

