The Clinical Benefit Rate (CBR) will be the proportion of patients with a CR, PR or Stable Disease according to RECIST criteria from the start to the end of Axitinib treatment (cf. CRF page 29).

PFIZER CONFIDENTIAL

Page 16 of 41

Patients who die, progress, or drop out for any reason prior to reaching a CR, PR or SD will be counted as non-responders in the assessment of CBR.

All assessments following an assessment of PD will be excluded from the derivation of CBR.

- Objective Response Rate (ORR) under TKI in 2nd line post Sunitinib

ORR is defined as the percentage of patients with complete response (CR) or partial response (PR) as best response under TKI treatment (cf. CRF page 36).

- Clinical benefice Rate (CBR) under TKI in 2nd line post Sunitinib

The Clinical Benefit Rate (CBR) will be the proportion of patients with a CR, PR or Stable Disease as best response under TKI treatment (cf. CRF page 36).

- Objective Response Rate (ORR) under mTOR in 2nd line post Sunitinib

ORR is defined as the percentage of patients with complete response (CR) or partial response (PR) as best response under mTOR treatment (cf. CRF page 36).

- Clinical benefice Rate (CBR) under mTOR in 2nd line post Sunitinib

The Clinical Benefit Rate (CBR) will be the proportion of patients with a CR, PR or Stable Disease as best response under mTOR treatment (cf. CRF page 36).

- Objective Response Rate (ORR) under IO in 2nd line post Sunitinib

ORR is defined as the percentage of patients with complete response (CR) or partial response (PR) as best response under IO treatment (cf. CRF page 36).

- Clinical benefice Rate (CBR) under IO in 2nd line post Sunitinib

The Clinical Benefit Rate (CBR) will be the proportion of patients with a CR, PR or Stable Disease as best response under IO treatment (cf. CRF page 36).

- Objective Response Rate (ORR) for Sunitinib received in 1st line

ORR is defined as the percentage of patients with complete response (CR) or partial response (PR) as best response under Sunitinib treatment (cf. CRF page 12 for patients included at time of Sunitinib initiation, cf. CRF page 26 for patients included at time of Axitinib initiation).

- Clinical benefice Rate (CBR) for Sunitinib received in 1st line

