8.1.1 Descriptive Methods

Descriptive analysis of qualitative and ordinal variables will comprise the number and percentage of each category. Percentages will be calculated on the number of all available data, excluding missing data.

Descriptive analysis of quantitative variables will present the mean, the standard deviation (SD) as well as the median, quartile 1, quartile 3, min and max values.

The 95% confidence intervals will be presented for main endpoints. The 'exact' Clopper-Pearson confidence interval will be provided to assess 2-sided 95% confidence interval for main binomial proportions (e.g. ORR rate).

The number of missing values will be reported in the results table for each variable.

8.1.2 Survival Analysis Methods

The survival functions (for PFS, TTF, TSF, OS) will be estimated with the Kaplan-Meier method. The survival function S(t) is the probability that the event (treatment discontinuation, death or progression) does not occur before a specified time.

This method will be applied to derive, survival curves, median event time and a 95% confidence interval for the median survival time (time at which half the analyzed patients have presented the event). Survival curves will give an idea of whether or not the groups are proportional (i.e. the survival functions are approximately parallel). For OS, the share of patients alive at 24 months will also be measured.

The log-rank test of equality across strata will be used to compare survival curves for categorical variables (sub-groups of interest). For continuous variables, a univariate Cox proportional hazard regression will be used.

For analyses of prognostic factors of survival time, multivariate Cox proportional hazard regressions will be performed.

8.1.3 Strategy of Variable Selection in a Cox Model for PFS Analysis

The strategy of selection of variables in multivariate models will consist in: *Step 1: Selection of initial factor*

In a first step, the association between the PFS and each potential factor will be analyzed using

- A Log-Rank test (PROC LIFETEST under SAS 9.4) for categorical factors. Kaplan-Meier curves will also be presented in order to give an idea of whether or not the corresponding groups are proportional (i.e. the survival functions are approximately parallel)
- a univariate Cox proportional hazard regression (PROC PHREG under SAS 9.4) for continuous factors

Only significant factors at the 25% threshold will be retained for the initial model.

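### SAP 6.1.2 counts unconfirmed responses toward ORR under axitinib, where the protocol requires confirmation at 4 weeks or later, and the SAP does not flag the change

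*SAP*

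**What the plan says.** **Protocol.** The secondary endpoint in 8.1.1 (Study endpoints) is the percentage of patients with "confirmed complete response (CR) or confirmed partial response (PR) according to RECIST criteria v1.1". Section 8.7.1 repeats the confirmed definition and explains it: "Confirmed responses are those that persist on repeat imaging study", at least "4 weeks after initial documentation of response". It sets the denominator as "relative to all patients who have baseline measurable disease". Patients who leave, progress or die before responding are non-responders.

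**SAP.** For axitinib, 6.1.2 states: "ORR is defined as the percentage of patients with complete response (CR) or partial response (PR) according to RECIST", over the period from start to end of axitinib. It keeps the protocol's non-responder rule and drops assessments made after a PD. It gives no confirmation requirement and no minimum interval. Section 8.2.2 adds only the exact Clopper-Pearson interval and the SU-AXI subgroup. Nothing elsewhere in the SAP restores confirmation.

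**Other rates in SAP 6.1.2.** ORR under other TKIs is the "percentage of patients with complete response (CR) or partial response (PR) as best response under TKI treatment", and the mTOR, IO and first-line sunitinib rates follow the same pattern. None has a confirmation rule or a stated non-responder rule. The general rule in SAP 8.1.1 is: "Percentages will be calculated on the number of all available data, excluding missing data".

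**The concern.** A secondary endpoint named in the protocol will be reported under the same name with a looser definition. A reader of the study report who knows the protocol would take the figure as confirmed ORR.

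Confirmation matters more than usual in this study. Protocol 8.9.4 acknowledges that physicians assess response by their own practice and that assessment can vary between sites. Requiring persistence on a second scan is the protocol's guard against a single favourable reading. Under the SAP, one such reading makes a responder.

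The SAP gives no reason. It carries over the neighbouring protocol sentence on non-responders but not the one on confirmation. The documents do not show whether this was a decision or an oversight.

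**Working it through.** **1. Figures in the plan.** The documents give no expected ORR, no confirmation rate and no precision target for ORR, so there is no ORR figure to reproduce. The one related input is the planned SU-AXI group of 350 in Protocol 8.5. Its stated precision of 5.2% reproduces as 1.96 × √(0.25/350) = 0.0524, but that figure is for PFS and TTF.

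**2. Direction.** Let N be the number of patients, R the number with at least one CR or PR before PD, and u the share of R that is not confirmed, either because the response did not persist or because there was no repeat scan.

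- SAP rate = R/N
- Confirmed rate on the same N = R(1 − u)/N
- Difference = uR/N, which is never negative

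Every confirmed responder is also a responder under the SAP. The two rates are equal only if every response is confirmed. If responses fail independently, the chance of at least one unconfirmed response is 1 − (1 − u)^R. With u = 5% that is 83.4% for R = 35 and 97.2% for R = 70.

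**3. Size, by assumption.** N = 350. The ORR levels and the values of u are assumptions, and counts are rounded to whole patients.

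| SAP rate (assumed) | u = 5% | u = 10% | u = 20% | u = 30% |
|---|---|---|---|---|
| 35/350 = 10.0% | 33: 9.4% | 31: 8.9% | 28: 8.0% | 25: 7.1% |
| 70/350 = 20.0% | 66: 18.9% | 63: 18.0% | 56: 16.0% | 49: 14.0% |
| 105/350 = 30.0% | 100: 28.6% | 95: 27.1% | 84: 24.0% | 73: 20.9% |

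The excess runs from (35 − 33)/350 = 0.6 points to (105 − 73)/350 = 9.1 points.

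Exact 95% intervals for the middle row:

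- 70/350: 15.9 to 24.6%
- 63/350: 14.1 to 22.4%
- 56/350: 12.3 to 20.3%
- 49/350: 10.5 to 18.1%

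**4. Denominator.** Measurable disease is an inclusion criterion (Protocol 8.2.1), the FAS is limited to eligible patients (SAP 5.1), and efficacy is analysed in the FAS (SAP 8.2.2). For the roughly 225 patients enrolled at axitinib start, the two denominators coincide. They could differ only among the roughly 125 enrolled at sunitinib start, for whom the criterion is not re-applied at axitinib start.

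If m of these had no measurable disease at that point, and all R responders did, the protocol rate would be R(1 − u)/(N − m). This exceeds R/N only when m/N > u. Example: m = 25 (25/350 = 7.1%) with 4 of 70 responses unconfirmed (5.7%) gives 66/325 = 20.3% against 20.0%.

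**5. Feasibility.** The axitinib follow-up form in Annex 1 records the date and response of each tumor assessment. Scans are expected about every 2 months (Protocol 8.2), which is longer than the 4-week minimum, so an ordinary next scan can confirm a response.

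**The case against.** The best defence is that the SAP was entitled to do this and that confirmation fits the design poorly. ORR is secondary, and the study is descriptive with no hypotheses (Protocol 8.5, SAP 4.1). Protocol 8.7 lets the SAP modify the plan. Imaging follows routine practice, so no repeat scan can be required, and SAP 6.1.1 itself foresees patients without regular assessments. A responder who stops axitinib for intolerance before the next scan cannot be confirmed, which is not the same as a response that failed. Variation between sites is already disclosed.

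Most of this stands. It supports reporting an unconfirmed rate as well, and it shows that a rule is needed for responders with no repeat scan. It does not support replacing the protocol definition without saying so.

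A reader might also infer more than the documents support:

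- **A breach of the amendment rule.** Protocol 8.7 calls for an amendment only for major changes to primary endpoints. This is an unflagged change to a secondary one.
- **A dropped denominator.** The SAP names its population, and measurable disease is an entry condition, so the two largely coincide. The axitinib initiation form has no measurable-disease field, so the protocol denominator could not be re-checked at that point in any case.
- **A certain excess.** The rates could be equal, and the denominator could in principle reverse the order (step 4 of the working).
- **A significant difference.** Only the assumed 30% case gives an interval that excludes 20.0%; the 10% and 20% cases include it. Comparing a point estimate with an interval from the same patients and nested outcomes is not a test.
- **Axitinib favoured over other second lines by confirmation.** Those rates are unconfirmed too. The long-term form holds one undated best-response tick per drug, so they cannot be confirmed.
- **Missing data certain to inflate those other rates.** The form offers NA as a category, nothing says it is treated as missing, and the text of SAP 8.2.2 on other second lines is incomplete here. The plan is unclear on this, which calls for a stated rule.

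**Conclusion.** The discrepancy is real. The protocol endpoint is confirmed ORR, and the SAP will produce unconfirmed ORR before PD under the same name, without notice or reason. On a common set of patients the SAP rate cannot be lower than the protocol rate, and it is higher as soon as one response is unconfirmed, which is very likely at the planned sample size.

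The size cannot be determined from the documents. The range of 0.6 to 9.1 points rests on an assumed ORR of 10 to 30%, 5 to 30% of responses unconfirmed, and 350 patients. It illustrates scale and is not a forecast. The issue affects a secondary, descriptive result and leaves the primary endpoints untouched. It should be corrected because the direction is predictable and the remedy is small.

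**What to change.** In SAP 6.1.2:

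1. Define the protocol endpoint as confirmed ORR under axitinib: a CR or PR still present at an assessment at least 4 weeks after first documentation and before PD, derived from the dated axitinib assessments.
2. Use all SU-AXI patients in the FAS as the denominator, and note that measurable disease is already an entry criterion.
3. Count patients with no assessment, and responders with no repeat scan, as not confirmed. Report the number of responders with no repeat scan separately, so that responses that failed can be told from those that could not be checked.
4. Keep the unconfirmed rate as a labelled supplementary result, and use it in any side-by-side with the TKI, mTOR, IO and sunitinib rates. Label those rates unconfirmed as well.
5. For those other rates, state that an NA or missing best response stays in the denominator as non-response, as for axitinib.
6. Record in the SAP how its ORR relates to the protocol definition.

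The cost is SAP wording and one derivation from data already collected. The headline ORR will be somewhat lower, and it will be conservative where routine practice provides no second scan.
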